- 1) *All-trans retinoic acid is a potent inhibitor of CYP7A1 in isolated human and rodent hepatocytes and reduces the bile acid pool size by 50% in bile duct ligated rat model of cholestasis resulting in significant reductions in liver injury (4-5).*
- 2) *Studies with ATRA administration to patients with PSC confirm that ATRA inhibits CYP7A1 (6).* This was observed through a Human Pilot studying the combination of ATRA and UDCA conducted at Yale and Mayo Clinics (HIC 1012007734). However, the full dose of ATRA, which is already in clinical use and FDA approved for management of acute promyelocytic leukemia, resulted in frequent side effects such as self-limited headaches and this indicates the need to evaluate efficacy of ATRA in patients with PSC while using lower doses.

Bibliography

1. *Allen et al. AJP 178:175, 2011.*
2. *Cai SY et al. Hepatology 60:300A, 2014.*
3. *Cai SY et al. 62:610A, 2015.*
4. *Cai SY et al. J.Lipid Res 51:2265, 2010.*
5. *He et al. Hepatology 53:548, 2011.*
6. *Assis DN et al. J Clin Gastroenterol. 51: e11-e16, 2017.*

4. Research Plan: Summarize the study design and research procedures using non-technical language that can be readily understood by someone outside the discipline. Be sure to distinguish between standard of care vs. research procedures when applicable, and include any flowcharts of visits specifying their individual times and lengths. Describe the setting in which the research will take place.

We propose an investigator-initiated efficacy trial of low dose ATRA monotherapy in a small group of patients with PSC to be conducted at the Yale Liver Clinics.

Study Design for an efficacy trial of low dose All-Trans Retinoic Acid (ATRA) in Primary Sclerosing Cholangitis (PSC)

- I. Objective: Evaluate effects of low dose ATRA therapy on serum alkaline phosphatase (ALP) over 24 weeks in adults with PSC.
- II. Study Design: Single-arm, open label study in PSC, comparing pre-treatment and post-treatment serum ALP levels in individual subjects and as a group.
- III. Number of Subjects: Goal of enrolling 20 adult subjects with PSC.
- IV. Dosage and Administration: ATRA 10 mg tablets will be taken with food once daily for 3 days and then increase to twice daily for the remainder of the study. With an option to dose escalate to 20 mg twice daily if Alk Phos does not reduce 5% or more after the first 12 weeks.
- V. Efficacy Evaluation
 - Primary Endpoint: Percent change of serum ALP from baseline to week 24

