 - Other Endpoints: The percent of patient who have the following from baseline to weeks 12 and 24, normalization of ALP, ALP < 1.5 x ULN and 50% reduction, reduction in C4, serum bile acids, ALT and serum ELF score improvement in fibrosis per Transient Elastography by at least 1 stage .
- VI. Safety Evaluation
 - Evaluate safety of ATRA with respect to frequency and severity of adverse events.
- VII. Facilities and Equipment
 - ATRA will be stored and dispensed for the study through the Yale New Haven Hospital Research Pharmacy.
 - Enrollment for the study will occur at the Yale Liver Center Clinics, [name] as well as the Yale Church Street Research Unit the CSRU.
 - Study visits will occur at the Yale Liver Center Clinics, [name] as well as the Yale Church Street Research Unit the CSRU.
 - Blood samples and research analyses will be stored and tested at the Yale Liver Center research building (TAC).
 - Clinical labs will be performed as per standard lab testing at the Yale New Haven laboratories.
- VIII. Screening Treatment and Follow up Visits

All below procedures are research related not standard of care.

 - Screening will be within 6 weeks of the Baseline Visit.
 - Subjects will be seen in clinic for screening, on treatment weeks 1, 4 and 12, end of treatment week 24, and follow up week 28.
 - Phone calls will be made to the patient on weeks 8 and 16.
 - If after week 12 the Alk Phos has not reduced 5% or more the dose will be doubled, and the wk 16 phone call will be replaced with an additional clinic visit.

- Approximately 60 mL or 4 tablespoons of blood will be drawn at each of the above clinic visits and again at week 48.
- Clinical Lab Testing: Serum ALP, total/direct bilirubin, AST, ALT, GGT, albumin, serum bile acids, lipid panel, basic metabolic panel, CBC, PT/INR.
- Research Lab Testing: Serum C4, MCP-1, IL-8, serum ELF.
- Additionally, blood will be stored in a de-identified way in order to perform potential genetic and other tests to understand the risks factors for the development of PSC.
- Imaging: Transient Elastography (Fibroscan) at Baseline Visit, and week 24.
- Complete and symptom based physical examinations and quality of life questionnaires will be performed at each visit.
- Symptoms will also be assessed by phone at weeks 8 and 16.

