- If at any point the Bilirubin, Alk Phos, AST or ALT increases 1.5 x over the patients baseline value, the ATRA will be held for 2 weeks. After 2 weeks the labs will be retested, and if the value is under 1.5 x the patients baseline value ATRA will be restarted at the same dose. If the value remains over 1.5 x the patients baseline value after 2 weeks the patient will be discontinued from the study treatment.

The screening and end of treatment visit (week 24) will take about 30-40 minutes, the on treatment visits (weeks 1, 4 , 12) and follow up 1 (week 28) will take about 20-30 minutes, follow up 2 (week 48) will take about 10 minutes, and the phone calls on week 8 and 16 will take about 10 minutes.

Women of childbearing age will need to use two forms of contraception, and have a negative pregnancy tests at screening and every study visit. A total of 6 pregnancy tests will be taken which will be paid for and provided by the research study.

5. Genetic Testing N/A

A. Describe

- i. the types of future research to be conducted using the materials, specifying if immortalization of cell lines, whole exome or genome sequencing, genome wide association studies, or animal studies are planned There is the potential for the banked specimens to be used for immortalization of cell lines, whole exome or genome sequencing, genome wide association studies, and animal studies.
- ii. the plan for the collection of material or the conditions under which material will be received blood samples will be collected by a trained phlebotomist.
- iii. the types of information about the donor/individual contributors that will be entered into a database We will use oncore.ynhh.org for the patient's information. Oncore will hold all of the current study data, and if samples are stored for future use. We will also use Epic for appropriate documentation.
- iv. the methods to uphold confidentiality The study personal will use oncore with encrypted laptops or university computers.

B. What are the conditions or procedures for sharing of materials and/or distributing for future research projects? The genetic material collected from the blood samples for future research projects may be shared within the network of physicians who have a professional working relationship with the PI and SubIs.

C. Is widespread sharing of materials planned? No

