- Headache – up to 86% of patients.
- Infections – up to 58% of patients.
- Risk of fetal malformations – ATRA is a pregnancy category D medication. There is a high risk of birth defects in babies born to mothers taking ATRA. Therefore, ATRA should not be used during pregnancy. If ATRA is used by a child-bearing aged mother, a negative pregnancy tests should be performed before taking the drug. A pregnancy test should also be done at every study visit. Two forms of contraception should be used while taking the drug, and for the month following discontinuation of the drug. Pregnancy should not be planned for up to 6 months after stopping the medication. Treatment should be stopped immediately if pregnancy develops.

Other than the pregnancy risks described above, it is not known if these side effects are seen as often or at all in patients who do not have leukemia and who have liver conditions such as PSC.

For those who develop headaches from ATRA, this symptom goes away within a few days for the majority of patients. If the subject experience a significant headache or similar symptom, but are otherwise healthy and still able to participate, we will reduce the dose of your medication so that you can tolerate the medication more easily.

In our previous Pilot of ATRA and UDCA in PSC the following frequency of adverse effects was observed as reported below (6). None were grade 3 or above:

TABLE 2. Reported Adverse Effects

Adverse Effects	Frequency (%)
Headache	63
Tinnitus	26
Diarrhea	16
Dry skin/mucus membranes	10
Myalgia	5
Anemia	5

Privacy risks are always a potential risk of a clinical study, but will be minimized by stringent procedures to ensure compliance with local and federal regulations regarding protected health information. We do not believe that this study poses an elevated risk for breach of subject privacy.

We do not believe subjects participating in the study will suffer from significant inconveniences, since they are currently under treatment by physicians at Yale, and thus are presenting to their usual centers of care, at which the study will be conducted.

11. Minimizing Risks: Describe the manner in which the above-mentioned risks will be minimized.

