3. Suggests that the research places subjects or others at greater risk of harm (including physical, psychological, economic, legal, or social harm) than was previously known or recognized.

Unanticipated Problems Involving Risks to Subjects or Others (UPIRSOs) may be medical or non-medical in nature, and include – but are not limited to – *serious, unexpected, and related adverse events and unanticipated adverse device effects*. **Please note** that adverse events are reportable to the IRB as UPIRSOs **only** if they meet all 3 criteria listed above.

These UPIRSOs/SAEs will be reported to the IRB in accordance with IRB Policy 710, using the appropriate forms found on the website. All related events involving risk but not meeting the *prompt* reporting requirements described in IRB Policy 710 should be reported to the IRB in summary form at the time of continuing review. If appropriate, such summary may be a simple brief statement that events have occurred at the expected frequency and level of severity as previously documented. In lieu of a summary of external events, a current DSMB report can be submitted for research studies that are subject to oversight by a DSMB (or other monitoring entity that is monitoring the study on behalf of an industry sponsor).

7. Plan for reporting adverse events to co-investigators on the study, as appropriate the protocol's research monitor(s), e.g., industrial sponsor, Yale Cancer Center Data and Safety Monitoring Committee (DSMC), Protocol Review Committee (PRC), DSMBs, study sponsors, funding and regulatory agencies, and regulatory and decision-making bodies.

For the current study, the following individuals, funding, and/or regulatory agencies will be notified (choose those that apply):

- All Co-Investigators listed on the protocol.
- Yale Cancer Center Data and Safety Monitoring Committee (DSMC)
- National Institutes of Health
- Food and Drug Administration (Physician-Sponsored IND # _____)
- Medical Research Foundation (Grant _____)
- Study Sponsor
- Other Data Safety Monitoring Board (DSMB) or Committee (DSMC)

The principal investigators will conduct a review of all adverse events upon completion of every study subject. The principal investigators will evaluate the frequency and severity of the adverse events and determine if modifications to the protocol or consent form are required.

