For more guidance on Adverse Event reporting and DSMPs, see IRB Policy 710 Reporting Unanticipated Problems Involving Risks to Subjects or Others, including Adverse Events

13. Statistical Considerations: Describe the statistical analyses that support the study design.

This is an exploratory Efficacy and Safety Human Pilot to determine if low dose ATRA is effective for reduction of cholestasis in patients with PSC and with a more favorable side effect profile with dose reduction. Although low dose ATRA monotherapy has not yet been studied in patients with PSC, we hypothesize a 30-40% reduction in serum Alkaline Phosphatase from baseline to week 24, which would require approximately 20 patients to achieve 90% power to detect a this difference at alpha of 0.05 using a two-sided one-sample t-test.

SECTION II: RESEARCH INVOLVING DRUGS, BIOLOGICS, RADIOTRACERS, PLACEBOS AND DEVICES

If this section (or one of its parts, A or B) is not applicable, check off N/A and delete the rest of the section.

A. RADIOTRACERS N/A

1. Name of the radiotracer: *Write here*
2. Is the radiotracer FDA approved? YES NO

If NO, an FDA issued IND is required for the investigational use unless RDRC assumes oversight.

3. Check one: IND# *Write here* or RDRC oversight (RDRC approval will be required prior to use)

B. DRUGS/BIOLOGICS N/A

1. If an exemption from IND filing requirements is sought for a clinical investigation of a drug product that is lawfully marketed in the United States, review the following categories and complete the category that applies (*and delete the inapplicable categories*):

Exempt Category 1: The clinical investigation of a drug product that is lawfully marketed in the United States can be exempt from IND regulations if all of the following are yes:

1. The intention of the investigation is NOT to report to the FDA as a well-controlled study in support of a new indication for use or to be used to support any other significant change in the labeling for the drug.	
2. The drug that is undergoing investigation is lawfully marketed as a prescription drug product, and the intention of the investigation is NOT to support a significant change in the advertising for the product.	

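### The dose texts conflict, promised monthly contact lapses between weeks 16 and 24, and the adverse-event summary is not specified by period or dose

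*Combined protocol and SAP*

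**What the plan says.** **Dose.** Section I.4 item IV starts subjects on 10 mg once daily for 3 days, then twice daily. For subjects whose ALP has not fallen by at least 5% over the first 12 weeks it continues "With an option to dose escalate to 20 mg twice daily". Item VIII of the same section states "If after week 12 the Alk Phos has not reduced 5% or more the dose will be doubled". The Guidelines for the Investigator (Section II.B, Drugs/Biologics, item 3) give a fixed 10 mg twice daily for every participant, set against the body-surface dose used in leukemia. They mention neither escalation nor reduction. Section I.10 says of significant headache that "we will reduce the dose of your medication so that you can tolerate the medication more easily". Under the liver-test rule at the end of the Section I.4 visit schedule, "the ATRA will be held for 2 weeks".

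**Contacts.** Section I.11 promises every subject monthly assessment, by visit or telephone. Section I.4 item VIII schedules clinic visits at weeks 1, 4, 12, 24 and 28 and calls at weeks 8 and 16; for subjects whose dose is doubled, the week-16 call becomes a visit. There is a further follow-up at week 48.

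**Safety summary.** Section I.4 item VI reads "Evaluate safety of ATRA with respect to frequency and severity of adverse events". Section I.13 gives part of the purpose as whether low-dose ATRA works "with a more favorable side effect profile with dose reduction". Under Section I.12, DSMP item 7, the principal investigators review adverse events as each subject completes, in order to "evaluate the frequency and severity of the adverse events and determine if modifications to the protocol or consent form are required".

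**The concern.** Two subjects with the same week-12 ALP could be treated differently depending on which section the treating investigator reads: doubled as a rule, doubled at discretion, or left unchanged. That affects exposure in the second half of treatment, and so both the week-24 ALP endpoint and the adverse events.

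The contact gap falls where it matters most for safety. If the dose is doubled after week 12, most of the time on that dose passes without a scheduled assessment. Section I.10 says "For those who develop headaches from ATRA, this symptom goes away within a few days for the majority of patients", so a headache early in the gap may be over well before the next scheduled question about it.

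The trial asks about tolerability at a reduced dose but lets the dose rise, fall or stop along the way. The protocol does not say how adverse events will be summarized against those changes. The per-subject safety review uses the same undefined frequency and severity, so the omission matters during the trial as well as at the end.

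**Working it through.** **1. Dose texts side by side, for a subject with less than a 5% ALP fall at week 12**

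| Place | Dose after week 12 |
|---|---|
| Section I.4 item IV | may rise to 20 mg twice daily |
| Section I.4 item VIII | is doubled |
| Section II.B, Guidelines for the Investigator | 10 mg twice daily, no change mentioned |
| Section I.10 (significant headache) | reduced, amount not given |

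The first two rows disagree on any reading. In the third, *fixed* may mean only that the dose is not scaled to body surface, since the sentence contrasts it with 45 mg/m²/day. Even then, the guidance omits both the escalation and the reduction found elsewhere.

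**2. Contact gaps**

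Scheduled contacts from baseline to the end of treatment: weeks 0, 1, 4, 8, 12, 16, 24.

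Gaps: 1, 3, 4, 4, 4 and 8 weeks. Only weeks 16-24 exceeds a month on treatment. After treatment the gaps are 4 weeks (24 to 28) and 20 weeks (28 to 48).

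Share of the possible doubled-dose period without a scheduled contact: (24 - 16)/(24 - 12) = 8/12 = 67%.

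Scheduled contacts after baseline: four up to week 12 (1, 4, 8, 12) and two after it (16, 24). The two 12-week halves are not equally observed.

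**3. How many subjects might escalate**

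The plan has no sample size or precision figure for adverse events to reproduce. Its 20 patients are for ALP (two-sided one-sample t-test, alpha 0.05, 90% power, 30-40% reduction), and no SD is stated. Solving the noncentral t for n = 20 gives a standardized effect of 0.764, hence an implied SD of 30/0.764 = 39.2 or 40/0.764 = 52.3 percentage points.

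Assume normality and a week-12 effect equal to the week-24 hypothesis. The share with less than a 5% fall is then:

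- Φ((5 - 30)/39.2) = 0.26, or 5.2 of 20
- Φ((5 - 40)/52.3) = 0.25, or 5.0 of 20

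Other assumed values give from 4% (mean fall 40%, SD 20; about 1 of 20) to 60% (no effect, SD 20; 12 of 20). The documents do not settle where in this range the trial will fall.

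**4. Precision of a split table**

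Exact (Clopper-Pearson) 95% limits for x of n: lower = the 0.025 quantile of Beta(x, n - x + 1); upper = the 0.975 quantile of Beta(x + 1, n - x).

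- 6/20 (30%): 11.9% to 54.3%
- 2/5 (40%): 5.3% to 85.3%

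The counts are illustrative; 5 is the escalated number from step 3. Such intervals describe and cannot compare doses. Escalated subjects would also be selected by ALP non-response.

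**The case against.** A reader might infer that the plan commits to one pooled 24-week frequency that hides the low-dose profile. It does not. Section I.4 item VI never says pooled, single or 24-week, and the Section II.B guidance continues adverse-event assessment to week 28. The fair criticism is that the summary is unspecified.

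A reader might also take the question in Section I.13 to concern 10 mg twice daily alone. The dose reduction there can equally mean reduction from the pilot's full dose, and item IV places escalation inside the low-dose design. At an assumed body surface of 1.6-2.0 m², 45 mg/m² is 72-90 mg a day. The starting 20 mg a day is then 22-28% of that, and an escalated 40 mg a day is 44-56%. On this reading a whole-regimen summary does answer the question. It would still not show what happened at the starting dose.

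Nor do the documents show that pooling would distort the result materially. That depends on the escalated share and on any added risk at the higher dose, neither of which is given. If escalation adds no events, there is no distortion.

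It would also be too strong to say that events in weeks 16-24 will be missed or that dose at onset will go unrecorded. Section I.11 asks subjects to return if there is any sign of adverse effects, and Section VI says investigators can be reached at all times. Section IV puts protocol-related treatment information on the case report forms, which are not supplied, and the safety review is done subject by subject at one site.

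These objections limit the analysis point to a reporting improvement. They leave the choice-versus-automatic conflict on escalation and the 8-week gap against a monthly promise untouched.

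**Conclusion.** Two contradictions are established from the text alone. Escalation is optional in one place, automatic in another and absent from a third. Monthly assessment is promised but not scheduled between weeks 16 and 24, an interval covering 67% of the time a doubled dose would be taken. Neither result needs an assumption beyond treating a month as about four weeks.

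The analysis point is smaller. The adverse-event summary has no stated period, dose or denominator, in a trial that asks about tolerability at a reduced dose and lets the dose change. The effect of mixing doses cannot be sized from the documents and may be zero. A split table is worth having because it costs almost nothing, but it will not support a formal comparison of doses.

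**What to change.** 1. Reconcile Section I.4 items IV and VIII, Section I.10 and the Section II.B Guidelines for the Investigator, so that all describe the same dose changes. The investigators decide which text governs; this review takes no view.
2. Reconcile Section I.11 with the visit schedule in Section I.4, either in the schedule or in the wording of the promise. That choice is also the investigators'.
3. Keep the overall adverse-event summary. Add a descriptive table that separates events with onset up to the week-12 dose decision from later ones, by dose at onset (including reduced or held). Show the number of subjects exposed in each row and exact 95% intervals, and note that the later period has fewer scheduled contacts.
4. Record onset date and dose at onset if the case report form does not already do so, so that events between visits and around dose changes are placed correctly.
5. Use the same split in the review under Section I.12, DSMP item 7.
6. Label any comparison with the pilot as descriptive. It ran 90 days at 45 mg/m² with ursodeoxycholic acid, which this trial requires to have been stopped for at least 3 months.

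The cost is wording changes, one table and at most two data items. A contact is added only if the investigators settle item 2 through the schedule.

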D. When and under what conditions will materials be stripped of all identifiers? Once the blood has been aliquoted into cryovials for storage no identifying information will be present. The link between the numerical code and the patient identifying information will be stored in oncore and relevant epic documentation only.

E. Can donor-subjects withdraw their materials at any time, and/or withdraw the identifiers that connect them to their materials? No. If the subject withdraws from the study after samples have been collected, the researchers may continue to use those samples, however, no future samples will be collected from the subject after they withdraw.

i. How will requests to withdraw materials be handled (e.g., material no longer identified: that is, de-identified) or material destroyed)? To withdraw from the study, the participant can call a member of the research team at any time and inform them of their intent to be removed. There will be no change to their medical treatment based on the decision to participate or not participate. The samples already collected will remain in storage, and no future samples will be collected.

F. Describe the provisions for protection of participant privacy We will use oncore.ynhh.org which will be accessed using encrypted laptops or Yale computers. All research records will be stored on either Yale provided Ironkey flash drives or in locked cabinets, access to identified data will be limited and the importance of confidentiality will be continuously impressed on the research team. The association between the code created after the samples are received and patient identity will be stored only in oncore and relevant Epic documentation. Once all data is collected, the data may be matched using the subject number and any identifiers will be removed from the data. All informed consent documents will be kept in a secure location separate from the data and electronically in Oncore and the patients chart in Epic.

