Despite being generally well tolerated in clinical practice for patients with leukemia, there are several potential toxic effects of oral ATRA including hyperlipidemia, exacerbation of coronary artery disease and arrhythmias, teratogenicity (pregnancy category D), hyperleukocytosis (in leukemic patients), and increased liver function tests (3). A unique adverse event from ATRA in APL involves retinoic acid syndrome, caused by capillary leak from leukemic cells and can be induced by ATRA (7). This does not appear to be a potential toxic effect in patients without APL. In routine clinical practice hepatotoxicity while on ATRA is uncommon, though if this develops it appears to have a similar profile to that of vitamin A toxicity, and resolves with discontinuation of the drug (3,8). One case report describes severe hepatotoxicity attributed to ATRA in a patient receiving the drug for APL (9).

There is little published data on the use of oral ATRA for patients with liver disease. The study by Bocher *et al.* (5) from 2008 evaluated oral ATRA (dosed at 45 mg/m² per APL treatment recommendations) for 90 days in patients with hepatitis from chronic hepatitis C virus infection. Subjects in this study did not demonstrate elevations in their aminotransferase levels or develop other evidence of hepatotoxicity (or other serious adverse effects). In fact, levels of AST and ALT diminished in all patients. Based on this literature data, and the encouraging results of pre-clinical studies, initial human with oral ATRA for 90 days was justified for purposes of a feasibility pilot study for patients with PSC. Since there is no clear data in humans to guide in the dosing of ATRA in cholestatic liver disease, this initial pilot used the FDA-approved daily oral dose of 45 mg/m² (2). The efficacy of ATRA and UDCA combination therapy is shown below regarding changes in alkaline phosphatase, AST, ALT, and reduction of bile acid intermediate C4.

The recorded adverse effect frequencies in the combination study pilot are shown below.

TABLE 2. Reported Adverse Effects

Adverse Effects	Frequency (%)
Headache	63
Tinnitus	26
Diarrhea	16
Dry skin/mucus membranes	10
Myalgia	5
Anemia	5

c. Marketing Experience

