- a. Targeted for enrollment at Yale for this protocol:

Goal is 20 adult subjects with PSC.

- b. If this is a multi-site study, give the total number of subjects targeted across all sites: **NA**

2. Indicate recruitment methods below. Attach copies of any recruitment materials that will be used.

 Flyers	 Internet/web postings	 Radio
 Posters	 Mass email solicitation	 Telephone
 Letter	 Departmental/Center website	 Television
 Medical record review*	 Departmental/Center research boards	 Newspaper
 Departmental/Center newsletters	 Web-based clinical trial registries	 Clinicaltrails.gov
 YCCI Recruitment database	 Social Media (Twitter/Facebook):	

Other: 1. Subjects may be referred or may self-refer from web 2. The use of the Liver Registry database HIC 0603001208REG. (in the consent form of the registry it asks if the patient "I agree to allow other Liver Center investigators to contact me directly to participate in specific research studies. Yes No "

* Requests for medical records should be made through JDAT as described at
<http://medicine.yale.edu/ycci/oncore/availableservices/datarequests/datarequests.aspx>

3. Recruitment Procedures:

- a. Describe how potential subjects will be identified.

Recruitment Procedures:

Describe how potential subjects will be identified.

Potential subjects will be identified from patients in the investigators' caseloads and may also be referred verbally, informally or formally by other physicians at Yale or community, to

contact or be contacted by one of the investigators. As the trial will be listed on clinicaltrials.gov, yalestudies.org and the YCCI clinical trials website there is a possibility that potential patients may contact the research staff after seeing the trial listing on the website.

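### Does 90% power with about 20 patients hold across the whole 30-40% range of ALP reductions?

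*Combined protocol and SAP*

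**What the plan says.** Section I.13 (Statistical Considerations) describes the study as an exploratory efficacy and safety pilot. It hypothesises "a 30-40% reduction in serum Alkaline Phosphatase from baseline to week 24, which would require approximately 20 patients to achieve 90% power" and continues "to detect a this difference at alpha of 0.05 using a two-sided one-sample t-test". It states no SD and does not say which reduction within the range was used for the calculation.

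The primary endpoint in Section I.4, item V is "Percent change of serum ALP from baseline to week 24". The enrolment target appears twice: "Goal of enrolling 20 adult subjects with PSC" (Section I.4, item III) and "Goal is 20 adult subjects with PSC" (Section III.1). No allowance for loss is given.

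Two other places bear on how many week-24 values there will be:

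- Section I.5.E, on banked material but worded for withdrawal from the study, says that "no future samples will be collected from the subject after they withdraw".
- Section I.4, item VIII provides that, when a rise in liver tests persists after a hold, "the patient will be discontinued from the study treatment".

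On earlier human data, the Safety and Efficacy text in Section II.B says: "The efficacy of ATRA and UDCA combination therapy is shown below regarding changes in alkaline phosphatase". Those results did not survive conversion of the file to text.

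**The concern.** For a fixed SD, the sample size needed for a given power depends on the size of the effect. One n and one power therefore cannot both be exact at 30% and at 40%. A reader who takes the 90% to hold throughout the range may be right, or may be overestimating the power at its lower end. If the calculation was done at 40%, the chance of missing a true 30% reduction would be about one in three rather than one in ten, and a non-significant result would mean something different in the two cases.

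The number described as required is also the number to be enrolled, so any patient without a week-24 ALP takes the study below its own figure. The plan also does not state that patients taken off treatment contribute their week-24 value to the test. This matters because the stopping rule includes ALP, which is the endpoint variable.

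**Working it through.** **Inputs.** From Section I.13: n = 20, power 0.90, two-sided alpha 0.05, one-sample t-test, reductions of 30 to 40%. The SD of percent change is not in the documents, so it is solved for and is not an estimate.

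**Formula.** With δ = mean change / SD, power = P(|T| > t(0.975, n−1)), where T is noncentral t with n−1 degrees of freedom and noncentrality δ√n.

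**Step 1: the plan's own figure.** Without an SD, n = 20 cannot be derived forwards. Solving backwards, 90% power at n = 20 needs δ = 0.7645 (noncentrality 0.7645 × √20 = 3.42). The implied SDs, in percentage points, are:

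- designed at 30%: 30 / 0.7645 = 39.2
- designed at 35%: 35 / 0.7645 = 45.8
- designed at 40%: 40 / 0.7645 = 52.3

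**Step 2: power and required n across the range, holding each SD fixed.**

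| n = 20 computed at | Implied SD | Power at true 30% | at 35% | at 40% | n for 90% power at 30 / 35 / 40% |
|---|---|---|---|---|---|
| 30% | 39.2 | 90.0% | 96.6% | 99.1% | 20 / 16 / 13 |
| 35% | 45.8 | 79.4% | 90.0% | 95.9% | 27 / 20 / 16 |
| 40% | 52.3 | 68.2% | 81.0% | 90.0% | 34 / 26 / 20 |

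For example, in the last row at a true 30%, δ = 30 / 52.3 = 0.573, the noncentrality is 0.573 × √20 = 2.56 and power is 68.2%. A simulation of 200,000 trials gave 68.1% for that cell and 79.5% for the 35% design point.

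**Step 3: dependence on the unknown SD.** With n = 20 and a true 30% reduction, power is 98.9% at SD 30, 95.3% at SD 35, 80.7% at SD 45 and 72.1% at SD 50. The documents do not place the SD within this span.

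**Step 4: loss.** At the design point (δ = 0.7645), power by number of evaluable patients is:

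| Evaluable | 20 | 19 | 18 | 17 | 16 |
|---|---|---|---|---|---|
| Power | 90.0% | 88.3% | 86.3% | 84.1% | 81.5% |

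Keeping 20 evaluable would take 20 / 0.9 = 22.2, so 23 enrolled, at an assumed 10% loss, or 20 / 0.8 = 25 at 20%. Both loss rates are assumptions, since the documents give none.

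**Step 5: patients taken off treatment.** The rule in Section I.4, item VIII ends study treatment, not study participation. The same item schedules the week-24 visit and blood draw for subjects in general, and nothing removes these patients from the primary endpoint. Read as written, a week-24 ALP is taken and used unless the patient has withdrawn from the study.

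**The case for a change.** The strongest case for a change is that Section I.13 makes a definite claim, with a named test, an alpha and a power. A protocol that makes such a claim should let the reader check it. The pilot label does not excuse an uninterpretable power, and the approximate wording does not help: if the design point was 40%, power at a true 30% is 68.2% for any n from 18 to 22. The earlier pilot tested ATRA with UDCA at 45 mg/m², so even if its ALP results supplied an SD, carrying that SD over to low-dose monotherapy would be an assumption worth stating. Rewording would cost one paragraph.

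The arithmetic in this argument is right, and the reporting gap is real: design point, SD and its source, and whether 20 means enrolled or evaluable are all unstated. What does not stand is the step from that gap to a defect in the design. The 68% requires the calculation to have been done at the most favourable end of the range, and the documents do not say that it was. Sizing at the low end is an ordinary way to handle a hypothesised range, and on that reading 90% is a minimum. Section I.13 can be faulted for not citing a source of variability, but not for having none, because the pilot ALP results to which Section II.B points are missing from the extracted text.

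**Conclusion.** The concern does not call for a change. The conditional figures are correct: power at a true 30% is 90%, 79% or 68% according to whether 20 was computed at 30%, 35% or 40%. They rest on a common SD across the range and on SDs solved from the plan's own claim. They do not show that the plan's 90% is wrong, and on the 30% reading no number would change.

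The lack of a margin is small. One or two losses cost 1.7 or 3.7 percentage points at the design point (90.0 − 88.3 and 90.0 − 86.3), within the looseness of an approximate requirement and an enrolment goal. Adding three to five patients with a rare disease at one centre, against a loss rate nobody has stated, is not clearly a gain.

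The analysis itself is unaffected. The one-sample t-test and its confidence interval use the SD observed in the trial, and a non-significant result would be read from that interval, not from the planning power. Patients taken off treatment remain in the week-24 schedule, so an analyst following the text would include them. What remains is missing detail in the sample-size paragraph of a study that calls itself exploratory. Following the plan as written does not produce a wrong result.
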